7.1	SAMPLE SIZE DETERMINATION	19
7.2	STATISTICAL METHODS	19
7.3	SUBJECT POPULATION(S) FOR ANALYSIS	20
8	SAFETY AND ADVERSE EVENTS	21
8.1	DEFINITIONS	21
8.2	RECORDING OF ADVERSE EVENTS	22
8.3	REPORTING OF SERIOUS ADVERSE EVENTS AND UNANTICIPATED PROBLEMS	23
8.3.1	Sponsor-Investigator reporting: notifying the Mayo IRB	23
8.3.2	Sponsor-Investigator reporting: Notifying the FDA	24
8.4	UNMASKING/UNBLINDING PROCEDURES	24
8.5	STOPPING RULES	24
8.6	MEDICAL MONITORING	24
9	DATA HANDLING AND RECORD KEEPING	24
9.1	CONFIDENTIALITY	24
9.2	SOURCE DOCUMENTS	24
9.3	CASE REPORT FORMS	25
9.4	RECORDS RETENTION	26
10	STUDY MONITORING, AUDITING, AND INSPECTING	26
10.1	STUDY MONITORING PLAN	26
10.2	AUDITING AND INSPECTING	26
11	ETHICAL CONSIDERATIONS	27
12	STUDY FINANCES	27
12.1	FUNDING SOURCE	27
12.2	CONFLICT OF INTEREST	27
12.3	SUBJECT STIPENDS OR PAYMENTS	27
13	PUBLICATION PLAN	28

14 REFERENCES.....	28
15 ATTACHMENTS	29

List of Abbreviations

LIST OF ABBREVIATIONS

AE	Adverse Event/Adverse Experience
ALT	Alanine Aminotransferase
AST	Aspartate Aminotransferase
CBC	Complete Blood Count
CFR	Code of Federal Regulations
CLDQ	Chronic Liver Disease Questionnaire
CRF	Case Report Form
DSMB	Data and Safety Monitoring Board
FDA	Food and Drug Administration
GCP	Good Clinical Practice
HIPAA	Health Insurance Portability and Accountability Act
IB	Investigator's Brochure
IL-4	Interleukin-4
IL-13	Interleukin-13
IND	Investigational New Drug Application
INR	International Normalized Ratio
IRB	Institutional Review Board
ISR	Injection Site Reaction
PHI	Protected Health Information
PI	Principal Investigator
SAE	Serious Adverse Event/Serious Adverse Experience
SC	Subcutaneous
SOP	Standard Operating Procedure
VAS	Visual Analogue Scale
VRS	Visual Rating Scale
PNRS	Pruritus Numerical Rating Score

Study Summary

Title	Dupilumab for the treatment of moderate to severe chronic hepatic pruritus: An open-label, single-arm, exploratory study
Running Title	Dupilumab for chronic hepatic pruritus
Protocol Number	19-002757
Phase	Phase II
Methodology	Open-label, single-arm, exploratory study
Overall Study Duration	18 months
Subject Participation Duration	22 weeks
Single or Multi-Site	Single-Mayo Clinic Florida
Objectives	To investigate the potential efficacy of dupilumab in the treatment of moderate to severe chronic hepatic pruritus.
Number of Subjects	12
Diagnosis and Main Inclusion Criteria	Male and/or female subjects 18 years or older with chronic pruritus of moderate to severe severity in the setting of intrahepatic or extrahepatic cholestatic liver disease. Chronic is defined as greater than 6 weeks of symptom duration. Pruritus severity is based on the peak pruritus numerical rating score (PNRS) of 4 (moderate severity).
Study Product, Dose, Route, Regimen	Dupilumab 600 mg SC week 0; then every 2 weeks x 18 weeks
Duration of Administration	18 weeks
Reference therapy	None-open label use of study drug
Statistical Methodology	A paired t-test will be used to evaluate mean differences before and after treatment at a p=0.05 significance level. The primary endpoint of the study is the mean percent change from baseline peak pruritus numerical rating score (PNRS) after 18 weeks. Correlations between the percent mean changes in the PNRS and quality of life outcome measures will also be analyzed.

1 Introduction

This document is a protocol for a human research study. This study will be carried out in accordance with the applicable United States government regulations and Mayo Clinic research policies and procedures.

1.1 Background

Chronic pruritus secondary to liver disease can negatively impact quality of life. These patients characteristically lack any skin inflammation, but are often severely symptomatic with chronic generalized involvement leading to significant quality of life impairments in sleep, daily activities, and personal relationships. To date, no clear pathophysiologic mechanism has been elucidated in chronic hepatic pruritus. No correlation has been found between plasma bile salt levels and endogenous opioid levels; while serum autotaxin levels are elevated in cholestatic liver disease, they are also increased in other pathological conditions which are not associated with pruritus. Standard therapy with bile salt binders, rifampin, sedating anti-histamines, partial opioid antagonists, selective serotonin reuptake inhibitors, narrowband UVB phototherapy, and serum plasma exchange is frequently ineffective and associated with dose limiting side effects. There exists a significant unmet clinical need for new therapies in the management of chronic hepatic pruritus.

1.2 Investigational Agent

Dupilumab, a licensed, FDA approved treatment for Atopic Dermatitis, is a human monoclonal IgG4 antibody that inhibits interleukin-4 (IL-4) and interleukin-13 (IL-13) signaling by specifically binding to the IL-4Ra subunit shared by the IL-4 and IL-13 receptor complexes. Dupilumab is a clear to slightly opalescent, colorless to pale yellow solution available as an injection of 300 mg/2 mL in a single-dose pre-filled syringe with needle shield for subcutaneous administration. Published results consistently showed that, compared with placebo, subcutaneous dupilumab 300 mg once weekly (qw) or every 2 weeks (q2w) significantly improved objective signs and symptoms of AD including pruritus, symptoms of anxiety and depression, and quality of life using dermatology-specific measures.

1.3 Preclinical Data

Recently, it has been established that IL-4 and IL-13 may directly activate sensory neurons in both mouse and human experimental models. Additionally, small diameter neurons mediating pruritus have been found to be enriched with IL-4 receptors and IL-13 receptors compared to other families of nociceptive and mechanoreceptive neurons. IL-4 has also been established to sensitize neurons to respond to previously subthreshold levels of histamine as well as other endogenous pruritogens. Therefore, inhibition of IL-4/IL-13 cytokine signaling on sensory neurons represents a potential therapeutic target in other conditions with chronic pruritus without overt skin inflammation.

1.4 Clinical Data to Date

Dupilumab, a fully human monoclonal antibody that blocks interleukin-4 and interleukin-13, has shown efficacy in the treatment of pruritus associated with moderate to severe atopic dermatitis. Notably, improvement of pruritus usually precedes clinically significant skin clearance suggesting other mechanisms beyond direct anti-inflammatory effects are of importance. Therefore we propose that dupilumab may have drug anti-pruritic effects independent of inflammatory effects.

1.5 Dose Rationale

The dose regimen of subcutaneous (SC) dupilumab selected for this study is 300 mg every 2 weeks for 18 weeks. All patients will get an initial loading dose of 600 mg (given as two 300 mg injections) at week 0. The administration of the loading dose of dupilumab will allow systemic concentrations to reach steady-state faster and reduce the time to onset of clinical effect. The dose of dupilumab for this study was based on the efficacy and safety results from multiple clinical trials that have led to the FDA approval of dupilumab at an initial dose of 600 mg then 300 mg every 2 weeks, for 18 weeks, for the treatment of atopic dermatitis.

1.6 Risks and Benefits

The postulated benefits of dupilumab include sustained immunomodulatory effects resulting in improvement of chronic hepatic pruritus. Mechanistically, as a biologic class medication, dupilumab has no hepatic metabolism; and since FDA approval for atopic dermatitis and asthma, no incidents of hepatic impairment have been reported

The following risks of dupilumab therefore felt to be low and manageable with the study protocol and do not outweigh the aforementioned benefits:

Hypersensitivity Reactions

Hypersensitivity reactions, including generalized urticaria and serum sickness or serum sickness-like reactions were reported in less than 1% of subjects who received dupilumab in clinical trials. This risk is idiosyncratic and will be minimized by administrating dupilumab in a supervised medical setting for the first treatment dose.

Conjunctivitis and Keratitis

Conjunctivitis and keratitis occurred more frequently in atopic dermatitis subjects who received dupilumab. Conjunctivitis was the most frequently reported eye disorder. Most subjects with conjunctivitis recovered or were recovering during the treatment period. Among asthma subjects the frequency of conjunctivitis was similar between dupilumab and placebo. Therefore, the development of keratitis appears related to the pathophysiologic state of AD and may not be entirely a direct drug effect. Keratitis was reported in <1% of the dupilumab group (1 per 100 subject-years) and in 0% of the placebo group (0 per 100 subject-years) in the 16-week atopic dermatitis monotherapy trials. In the 52 week dupilumab + topical corticosteroids (TCS) atopic

dermatitis trial, keratitis was reported in 4% of the dupilumab + TCS group (12 per 100 subject-years) and in 0% of the placebo + TCS group (0 per 100 subject-years). Most subjects with keratitis recovered or were recovering during the treatment period. Among asthma subjects the frequency of keratitis was similar between dupilumab and placebo. Subjects will be advised to report new onset or worsening eye symptoms and will be appropriately assessed and treated.

Eosinophilic Conditions

Patients being treated for asthma may present with serious systemic eosinophilia sometimes presenting with clinical features of eosinophilic pneumonia or vasculitis consistent with eosinophilic granulomatosis with polyangiitis, conditions which are often treated with systemic corticosteroid therapy. These events may be associated with the reduction of oral corticosteroid therapy. Physicians should be alert to vasculitic rash, worsening pulmonary symptoms, cardiac complications, and/or neuropathy presenting in their patients with eosinophilia. Cases of eosinophilic pneumonia and cases of vasculitis consistent with eosinophilic granulomatosis with polyangiitis have been reported with dupilumab in adult patients who participated in the asthma development program. A causal association between dupilumab and these conditions has not been established.

Reduction of Corticosteroid Dosage

Reductions in corticosteroid dose, if appropriate, will be gradual and performed under the direct supervision of a physician.

Parasitic (Helminth) Infections

Patients with known helminth infections were excluded from participation in clinical studies. It is unknown if dupilumab will influence the immune response against helminth infections. This risk will be minimized by excluding enrollment of study participants with known tapeworm or roundworm infections.

2 Study Objectives

Primary Objective: To investigate the potential efficacy of dupilumab in the treatment of adults with moderate to severe chronic hepatic pruritus.

3 Study Design

3.1 General Description

This is a 22-week (2 week screening, 18-week treatment period followed by a 2 week follow-up), phase II, open label, exploratory study to investigate the potential efficacy of FDA approved dupilumab in the treatment of adults with moderate to severe chronic hepatic pruritus. Subjects will be screened at outpatient clinic visit appointments and interested qualified subjects will be consented and offered participation in this trial. Once consent has been obtained, baseline values will be established and subjects will begin treatment and follow-up for the next 20 weeks. A final visit will be needed for evaluation and questionnaire completion.

3.2 Number of Subjects

A target of 12 subjects will be enrolled.

3.3 Duration of Participation

Each subject's participation in the study will be up to 22 weeks including the screening period.

3.4 Primary Study Endpoints

The primary endpoint of the study will be the mean percent change in the Peak Pruritus Numerical Rating Score (PNRS) before and after 20 weeks of treatment with dupilumab. Pruritus severity is measured using the peak NRS assessed as a single, self-completed item that assesses the intensity of peak (worst) pruritus during the past 24 hours using the query: "On a scale of 0 to 10, with 0 being 'no itch' and 10 being 'worst itch imaginable', how would you rate your itch at the worst moment during the previous 24 hours?". The baseline and treatment mean peak PNRS will be the average of the daily score for 7 days before treatment and then after the first treatment dose self-assessed by patients daily and then averaged for 7 days.

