7.2 Statistical Methods

Descriptive Statistics

Continuous variables will be summarized using the sample mean, median, standard deviation, interquartile range, and range. Categorical variables will be summarized using number and percentage of patients.

Handling of Missing Data

In the event of any unexpected missing data, this will be imputed using the last observation carried forward method.

Multiplicity

Since this is an exploratory pilot study, no adjustment for multiple testing will be undertaken.

Primary Hypothesis: For subjects with chronic hepatic pruritus, treatment with dupilumab will improve the PRNS after 1 weeks of treatment.

As previously described, the PRNS will be assessed on a daily basis for each patient. Separately for the 7 days prior to treatment (i.e. pre-treatment), the first 6 weeks of treatment (i.e. weeks 1 to 6), the second six weeks of treatment (i.e. weeks 7 to 12), the third six weeks of treatment (i.e. weeks 13 to 18), and the final two weeks of treatment (i.e. weeks 19 and 20), the mean of these daily PRNS measures will be calculated for each patient, resulting in a pre-treatment, week 6, week 12, week 18, and week 20 mean PRNS measurement for each patient. We will summarize the percentage change in PRNS values from pre-treatment to week 6, week 12, week 18, and week 20 using the aforementioned descriptive statistics. Additionally, we will estimate the proportion of patients whose mean PRNS value improves by 3 or more point, and by 4 or more points, from pre-treatment to each of the week 6, week 12, week 18, and week 20 time periods. Comparisons of mean PRNS between the pre-treatment time period and each of the week 6, week 12, week 18, and week 20 time periods will be made using a paired Wilcoxon signed rank test.

For secondary endpoints (VRS, 5D pruritus score, and CLDQ), these will be compared between the pre-treatment and follow-up time points using a paired Wilcoxon signed rank test. Although focus will be more on descriptive summaries rather than statistical significance due to the pilot nature of the study, p-values less than 0.05 will be considered as statistically significant.

Interim Analysis

There will not be any interim analysis given the low risk profile of the study formulation and the pilot nature of the study.

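### The primary result is not uniquely defined: 18 or 20 weeks, paired t-test or Wilcoxon, and a percent-change endpoint for which only raw scores are tested in 7.2

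*Combined protocol and SAP*

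**What the plan says.** **Time.** Section 3.4 gives the primary endpoint as the "mean percent change in the Peak Pruritus Numerical Rating Score (PNRS) before and after 20 weeks of treatment with dupilumab". The Statistical Methodology row of the Study Summary says: "The primary endpoint of the study is the mean percent change from baseline peak pruritus numerical rating score (PNRS) after 18 weeks". The primary hypothesis in 7.2 gives a third time, 1 week, which is probably a typing error.

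**Test.** The Study Summary says: "A paired t-test will be used to evaluate mean differences before and after treatment at a p=0.05 significance level". Section 7.2 instead plans "Comparisons of mean PRNS between the pre-treatment time period and each of the week 6, week 12, week 18, and week 20 time periods", which "will be made using a paired Wilcoxon signed rank test". None of the four periods is named as primary.

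**Variable.** The Study Summary and 3.4 both define the endpoint as percent change. In 7.2, percent change appears only in a descriptive commitment: "We will summarize the percentage change in PRNS values from pre-treatment to week 6, week 12, week 18, and week 20". The Wilcoxon test there is applied to the mean score itself (spelled PRNS in 7.2).

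**Averaging window.** In 3.4 the on-treatment score is "self-assessed by patients daily and then averaged for 7 days", without saying which 7 days. In 7.2 the week-18 value is the mean of all daily scores in weeks 13 to 18, and the week-20 value is the mean over weeks 19 and 20.

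**The concern.** Two analysts who each follow the plan faithfully could report different primary results, because time, test, variable and window are each open to more than one reading. The trial is open-label and the outcome is self-reported, so the reading should not be open to choice once the data are known.

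The exploratory label and the waived multiplicity adjustment do not settle this. They say how much weight a p-value carries, not which number is the primary result. Section 7.2 still states a primary hypothesis and a 0.05 threshold. Section 13 counts the results-posting deadline from the last data collection for the primary outcome, and expects favourable results to help justify a larger trial.

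**Working it through.** **1. Does any other text break the tie?** There is no plan figure to reproduce: 7.1 reports no power calculation, and no effect size or SD is given. The check starts with the text.

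| Item | Study Summary | 3.4 | 7.2 |
|---|---|---|---|
| Time | 18 weeks | 20 weeks, called treatment | weeks 6, 12, 18, 20; none primary |
| Variable | percent change | percent change | percent change summarised; raw mean tested |
| Test | paired t-test of mean differences | none | Wilcoxon signed-rank |
| Window | not stated | 7 days, not identified | 6-week or 2-week block |

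- Sections 3.1 and 5.2 give 18 weeks of treatment. The supply dispensed under 6.2 and 6.4 covers 12 + 6 = 18 weeks. Sections 3.1 and 6.6 treat week 20 as follow-up. Section 3.4 and the week 19-20 label in 7.2 disagree with these and must be reconciled with them.
- The Study Summary plans to correlate percent change in PNRS with quality of life, but 3.5 and 6.5 collect the follow-up CLDQ at week 18. A week-20 primary endpoint would not match it in time.
- Section 3.5 uses weekly averages for the responder endpoints, whereas 7.2 computes responders from the multi-week means. The window conflict therefore reaches beyond 3.4.
- No passage gives an order of precedence.

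The remaining steps are illustrations on assumptions that are not in the documents.

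**2. Time and window.** Assume a baseline of 7 and a fall of E(t) = 4(1 − exp(−t/τ)) points, with τ = 2, 4 or 6 weeks. Percent change is the average of E over the window, divided by 7.

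| Reading, effect persisting | τ=2 | τ=4 | τ=6 |
|---|---|---|---|
| 7 days ending week 18 | 57.1% | 56.4% | 54.0% |
| Weeks 13-18 | 57.1% | 55.7% | 52.3% |
| Weeks 19-20 | 57.1% | 56.6% | 54.7% |
| 7 days ending week 20 | 57.1% | 56.7% | 54.9% |

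The largest spread is at τ=6: 54.9 against 52.3, or 2.7 points before rounding.

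Now let the effect wane exponentially from week 18, with time constant 2, 4 or 8 weeks. The weeks 19-20 value becomes 36.1/45.0/50.6% (τ=2), 35.7/44.5/50.0% (τ=4) and 34.3/42.7/48.0% (τ=6). The gap between 7.2's own week-18 and week-20 values runs from 57.1 − 36.1 = 21.0 points down to 52.3 − 48.0, or 4.2 before rounding. If week 18 is a 7-day mean, the smallest gap is 54.0 − 48.0 = 6.0.

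For scale, the 95% CI half-width with n = 12 is t(0.975, 11 df) × SD/√12 = 0.635 × SD. That is 15.9 points at SD 25 and 22.2 at SD 35.

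**3. Choosing the time, or the time and the test, with no true change.** The exact two-sided signed-rank test with n = 12 rejects when W ≤ 13, with size 4.248%. The simulation used normal change scores and 200,000 replicates. The correlation range starts at 0.5 because a shared baseline with equal error variances alone produces that value.

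| Correlation, week 18 with week 20 | 0.5 | 0.6 | 0.7 | 0.8 | 0.9 |
|---|---|---|---|---|---|
| Either time, signed-rank | 7.9% | 7.8% | 7.4% | 7.0% | 6.3% |
| Either time, either test | 9.9% | 9.7% | 9.3% | 8.6% | 7.8% |

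At one fixed time with a choice of test, the rate is 5.3-5.5%. A daily-diary model gave correlations of 0.71-0.87 and 6.6-7.4% for either time by signed-rank.

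**4. t-test against signed-rank at one time.** The assumptions are baseline mean 7 and SD 1.5 (limited to 4-10), change SD 2, scores limited to 0-10, and 100,000 replicates.

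| True mean fall | 0 | 1.0 | 1.3 | 1.6 | 2 | 3 | 4 |
|---|---|---|---|---|---|---|---|
| Verdicts differ at 0.05 | 1.7% | 6.9% | 7.5% | 6.6% | 4.2% | 0.2% | 0.001% |

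The t-test is significant more often than signed-rank: 39.9 against 35.1% at a fall of 1.0, 59.0 against 53.5% at 1.3, and 75.8 against 70.6% at 1.6.

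**5. Raw against percent change.** With baseline uniform on 4-10, change SD 2 and 4,000 trials per scenario, the signed-rank verdict on raw change differs from that on percent change in 1.6, 5.2, 6.2 and 3.0% of trials at falls of 0, 1.0, 1.5 and 2.0 points.

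**The case against.** The strongest reply is that little turns on this. Section 7.2 commits to percent-change summaries and a Wilcoxon test at all four periods and puts the focus on description, so a reader would see both week 18 and week 20. That stands, and it limits the harm. What stays open is which result is called primary.

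It can also be said that the variable mismatch is not a contradiction, because the endpoint is estimated on the percent scale and the hypothesis of improvement is tested on the raw scale. This is partly fair: percent change is reported. Yet 7.2 attaches no test to it, and the Study Summary's t-test of mean differences does not clearly test it either.

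Several limits on the size stand:

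- The 4-21 point gap requires waning to begin at week 18. The documents do not say whether the last injection falls at week 16 or week 18. If it falls at week 18, weeks 19-20 are a dosing interval.
- The rates in step 3 count significant worsening as well as improvement. By symmetry, favourable false positives are about half: 6.3/2 to 7.9/2, roughly 3.2-4.0%, against 4.25/2 = 2.1%.
- The diary model does not support the upper end, which sits at correlation 0.5.
- Disagreement between the tests is confined to small effects. At the 4-point fall assumed in step 2 it almost vanishes.
- Moving the primary time from week 18 to week 20 shifts the posting deadline by only about two weeks.

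The window is the weakest of the four points, since 3.4 is incomplete rather than plainly opposed to 7.2, although the weekly averages in 3.5 strengthen it. None of this ranks the conflicting statements. A claim that 7.2 governs because it is more detailed has no support in the text, and 7.2 names no primary period anyway.

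**Conclusion.** The concern holds. The conflicts of time (18 against 20 weeks) and test (paired t-test against Wilcoxon) are explicit, 7.2 tests only raw mean PNRS although the endpoint is percent change, and nothing states which text takes precedence. This conclusion rests on the wording alone.

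The consequence is modest. Under the assumed models, the choice of reading moves the estimate by less than 3 points if the effect persists. If it wanes after week 18, the shift is at most about as large as the sampling uncertainty with 12 patients. False-positive inflation from choosing the time, or the time and test, reaches at most about 10%, two-sided. The point should be fixed because the plan as written leaves the primary result open to choice after the fact and the correction is cheap. Confidence in the conflict is high; the sizes are illustrations.

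**What to change.** Before analysis, put one time point, one averaging window with its exact days, one variable and one test in identical words in the Study Summary, 3.4 and 7.2, so that the test addresses the stated endpoint. Report the primary estimate with a 95% CI, and label every other period secondary or descriptive. Week 18 agrees with the Study Summary and with the 18-week treatment period, but any single consistent choice resolves the conflict. Correct the 1-week time in the primary hypothesis. Reconcile the description of weeks 19-20 in 3.4 and 7.2 with 3.1, 5.2, 6.2, 6.4 and 6.6.

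The cost is a wording amendment, with no extra patients or data. The sponsor gives up the freedom to choose among readings. If a 7-day window is chosen, it is noisier than the 6-week block: in the diary model the SD of change was 10-24% larger (for example 1.92 against 1.74, and 1.46 against 1.18).

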5.2 Treatment Regimen

All study participants will receive dupilumab 600 mg SC at week 0; then 300 mg SC every 2 weeks for a total of 18 weeks.

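### The primary endpoint is set at 20 weeks in section 3.4 and at 18 weeks in the Study Summary; section 7.2 names no primary time point and counts weeks 19-20 as treatment in an 18-week regimen

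*Combined protocol and SAP*

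**What the plan says.** The primary endpoint is placed in time in three parts of the document.

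- Section 3.4 takes the change in peak PNRS "before and after 20 weeks of treatment with dupilumab". It averages daily scores over 7 days, both before treatment and afterwards.
- The Study Summary (Statistical Methodology) gives the primary endpoint as the "mean percent change from baseline peak pruritus numerical rating score (PNRS) after 18 weeks".
- The primary hypothesis in section 7.2 is that "treatment with dupilumab will improve the PRNS after 1 weeks of treatment" (PRNS is evidently PNRS).

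Section 7.2 then forms period means for weeks 1-6, 7-12, 13-18 and 19-20, and describes the last of these as "the final two weeks of treatment (i.e. weeks 19 and 20". Comparisons between pre-treatment and "each of the week 6, week 12, week 18, and week 20 time periods will be made" with a signed rank test. None of the four is marked as primary.

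The design sections describe a shorter treatment period. Section 3.1 has an "18-week treatment period followed by a 2 week follow-up", section 5.2 gives the loading dose and "then 300 mg SC every 2 weeks for a total of 18 weeks", and the Study Summary lists 18 weeks of administration. Section 6.6 treats the week-20 visit as follow-up and labels its PNRS post-treatment.

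**The concern.** A trial should have one primary number that anyone following the plan would compute in the same way. Here an analyst following 3.4 would report a score from the follow-up visit, and one following the Study Summary would report a score from the end of treatment. The statistical section, where one would look for the answer, lists four comparisons and ranks none of them. The choice could then be made after the data are seen.

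The choice also affects other parts of the plan. The Study Summary intends to correlate PNRS change with quality of life, and the CLDQ is collected only at baseline and week 18. Section 13 ties the posting of results to final data collection for the primary outcome, and that date depends on which week is primary. The same section says that favourable results could support a larger trial, so its planners would need one identifiable estimate.

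**Working it through.** The plan has no power calculation to reproduce (section 7.1 says that none was done). The check is a timeline.

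**1. Length of participation.** Inputs from 3.1: screening 2 weeks, treatment 18, follow-up 2. Sum: 2 + 18 + 2 = 22 weeks, which reproduces the stated 22 weeks. With 20 weeks of treatment the sum would be 2 + 20 + 2 = 24 weeks, which does not fit.

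**2. Drug supply.** A 12-week supply is dispensed at week 0 (6.2) and a 6-week supply at week 12 (6.4): 12 + 6 = 18 weeks. No supply is listed for a further two weeks.

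**3. Days covered by each candidate measure.** Taking week n as day 7n:

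- 3.4, 7 days to week 20: days 133-140
- 7.2, weeks 19-20: days 126-140
- Study Summary time point with 3.4's 7-day window: days 119-126
- 7.2, weeks 13-18: days 84-126, since 12 x 7 = 84; length 126 - 84 = 42 days

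The 7-day windows for weeks 18 and 20 share no diary days, because one ends at day 126 and the other starts at day 133. At week 18 the 7.2 window is 42 / 7 = 6 times as long as the 3.4 window. Two time points (18, 20) times two windows (3.4, 7.2) give 2 x 2 = 4 candidate primary results.

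**4. Which time point the rest of the plan supports.**

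- Week 18: the Study Summary; the treatment length in 3.1 and 5.2; the PNRS responder endpoints in 3.5 (weeks 6, 12, 18); the 5D and CLDQ collection (baseline and week 18).
- Week 20: section 3.4; the additional week-20 comparison and responder summaries in 7.2; the final diary collection in 6.6.

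**5. Which window it supports.** Baseline is a 7-day average in both 3.4 and 7.2, and 3.5 uses weekly averages. A 7-day window at week 18 matches both. A six-week mean does not.

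**The case against.** The strongest reply is that little depends on the label. This is an exploratory study of 12 subjects with no power calculation, and 7.2 says that the "focus will be more on descriptive summaries rather than statistical significance". Percent change will be summarised at weeks 18 and 20 in any case, so a reader will see both. That stands, and it limits the seriousness of the point. It does not excuse two definitions of one primary endpoint.

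A second reply is that 7.2's hypothesis was meant to say 18 weeks, in which case it agrees with the Study Summary and only 3.4 is out of line. That is probably right, and it supports choosing week 18. The printed text still does not say so.

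A third reply is that a last dose at week 18 would have a dosing interval running to week 20, making weeks 19-20 arguably on treatment. The week of the last dose is not stated, so this cannot be excluded. But 3.1 and 6.6 call that period follow-up and post-treatment, so the labels conflict on either reading.

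A reader might also infer more than the documents support:

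- *That week 1 is a third rival time point.* The plural wording suggests a dropped digit, 7.2 computes no week-1 mean, and no week-1 visit exists.
- *That the last dose is at week 16.* This follows from the supply only if a 12-week supply means six dosing occasions. No syringe count is given.
- *That week 18 is preferable because it stays within one 14-day dosing interval.* After a week-16 dose (day 112), the week-18 visit at +2 days falls on day 128, and 128 - 112 = 16 days.
- *That a week-20 result would be biased in a known direction.* Section 7.1 assumes no spontaneous improvement, but there is no control arm and 5.6 permits other itch treatments. The plan gives no itch data after the last dose, and days since dosing do not measure a shift in score.

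**Conclusion.** The inconsistency is certain on the current text: 20 weeks in 3.4 against 18 in the Study Summary, four tested periods in 7.2 with none primary, and two averaging windows. Calling weeks 19-20 treatment, in both 3.4 and 7.2, conflicts with the 18-week treatment period and the post-treatment label in 6.6.

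Its size can be stated only as ambiguity: four candidate primary results. How far the reported percent change would differ between them, and in which direction, cannot be derived from the documents. The point should be corrected, but it does not undermine the study.

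The preference for week 18 rests on the stated regimen, the Study Summary, section 3.5 and the week-18 CLDQ needed for the planned correlations. It does not depend on which week the last dose is given. That 1 week is an error for 18 is an inference, though a likely one; the conflict between 18 and 20 stands without it.

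**What to change.** - In 3.4, the Study Summary and the 7.2 primary hypothesis, name week 18 as the single primary time point. In 3.4 this replaces 20 weeks; in 7.2 it corrects 1 week to 18 weeks.
- State one averaging window in all three places: the mean of daily PNRS over the 7 days to week 18, compared with the 7-day baseline.
- In 7.2, mark the week-18 comparison as primary and the other periods as supportive.
- In 3.4 and 7.2, stop describing weeks 19-20 as treatment. Call them post-treatment follow-up and report them separately.

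Sections 3.1 and 6.6 already read this way and need no change. The cost is a wording amendment, with no added visits, patients or assessments. The daily diary already supplies the scores for the 7-day window, and the sample size of 12 is unaffected because it does not come from a power calculation.
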